Experimental Design: The proposed design is a randomized, double-blind, two-arm trial of pregnenolone and placebo to determine the possible analgesic effects in OEF/OIF Veterans with chronic low back pain. The total study duration is 8 weeks (6 study visits followed by two-follow up phone calls). All patients will monitor pain symptoms for one week with pain diaries, followed by a 1-week placebo-only lead-in period, 90 subjects will be randomly assigned to one of two groups. Of these subjects, 45 subjects will receive pregnenolone, and 45 subjects will receive placebo for 4 weeks (in addition to the taper period of 5 days). Patient interview assessments and laboratory studies will be performed at each interview time point. Pregnenolone, allopregnanolone and other neurosteroid metabolites will be determined by gas chromatography / mass spectrometry (GC/MS), proceeded by high performance liquid chromatography (HPLC). Those subjects randomized to pregnenolone will receive this neurosteroid on the following schedule:

- Pain symptom monitoring with pain diaries for 1 week, then
- Placebo lead-in phase 0 mg in two doses (0 mg, PO, BID) for 1 week, then
- Pregnenolone 100 mg in divided doses (50 mg, PO, BID) for 1 week, then
- Pregnenolone 300 mg in divided doses (150 mg, PO, BID) for 1 week, then
- Pregnenolone 500 mg in divided doses (250 mg, PO, BID) for 2 weeks.

Dosing: Pregnenolone fixed escalating up to 500mg/day will consist of the following schedule:

Visit 1 (week 0, screening visit) and pain symptom assessment

Visit 2 (week 1) placebo lead-in (all participants)

Visit 3 (week 2, baseline visit): 50mg PO, BID x 1 week,

Visit 4 (week 3): 150mg PO, BID x 1 week,

Visit 5 (week 4): 250mg PO, BID for two weeks.

Visit 6 (week 6): No medication will be dispensed; study medication will be tapered by 100mg per day and then discontinued. The FDA has reviewed this protocol and issued an Investigational New Drug number (IND #114,799) for this randomized controlled trial utilizing the pregnenolone doses above for low back pain, and has provided a formal permission to proceed letter for this study. In addition, [name] (the PI's primary mentor on this VA funded Career Development Award) currently holds FDA IND numbers for the use of pregnenolone for treatment of schizophrenia (IND #71,768), PTSD (IND #73,099) and TBI (IND #78,270).

Methodology for Neurosteroid Identification and Quantification:

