Any incident regarding theft/loss of data, authorized access of sensitive data or storage devices or non-compliance with security controls will be addressed according to VA policy (VHA Handbook 1200.05, 10j; 1058.01 11.a; 6500, Appendix D and 6500.2) and will be reported to Durham VAMC PO and ISO immediately using the following: [contact].

Study members who are initially part of the study team, but leave the study team for whatever reason will no longer have access to participant study data.

DATA ANALYSIS AND STATISTICAL CONSIDERATIONS

Statistical Methods

Analysis of treatment effects will use the mixed-models approach to repeated-measures analysis of variance (SAS Institute, Cary, NC) with baseline and endpoint scores as dependent variables, time as a within-subject repeated measure, and treatment group (pregnenolone or placebo) as a between-subjects fixed factor. The primary analyses for this will be based on an intention-to-treat principle that will include in the analyses all randomized subjects. The primary efficacy outcome variable is the weekly mean of the average pain scores (0 – 10 numeric rating pain score recorded daily from patient) after study drug initiation. These are obtained over time, and thus we will use mixed effects models with random intercepts to account for subject effects and the correlation among repeated measurements within a subject. Models will be developed which include as independent variables the treatment group and the baseline pain score. Thus, the effect of the intervention will be assessed by examining the significance of the slope β_1 coefficient for intervention in the following model:

$$P_{it} = \beta_0 + b_{0i} + \beta_1 Int + \beta_2 BaseP + \beta_3 t + e_{it}$$

where P_{it} is the mean weekly pain score for the i^{th} individual at time point t , β 's denote fixed effects, b_{0i} is the random intercept for the i^{th} individual, and e 's are random errors. Patients who are withdrawn from the study because of side effects will only be included in outcome assessments in which they participated. The mixed effects models can handle incomplete panels of information. All tested hypotheses will be considered statistically significant if the 2 sided p value is ≥ 0.05 unless otherwise specified.

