Secondary analyses will include the following assessments. Assessment of changes in mood, anxiety, sleep, working memory, executive function, and pain interference (BDI, DTS, Tower of London, Digit Sequencing Task, BPI interference, PGI, AIS) will be analyzed via a repeated measures analysis similar to analyses for primary outcome assessments. Categorical analyses of patient response (30% improvement, 50% improvement) will be evaluated via a comparison of proportions using Fisher's exact test. Time to event analyses will also be performed, to examine the time to 30% and time to 50% reduction in 24 hour average pain score, using daily pain score data. These analyses will be performed by calculating Kaplan-Meier survival curves. Changes in physical function, mental health, cognitive symptoms and back pain-related disability will be assessed using ANCOVA models. Safety will be assessed by comparing the incidence of major and minor side effects (defined in human subjects section below) in the study drug vs. placebo groups, using Fisher's exact tests. Path analysis will be used to perform a preliminary assessment of whether any pain reduction effect is independent of possible effects of study drug on anxiety and mood.

Missing data: The mixed models used to evaluate the continuous response variables are able to handle moderate amounts of missing data provided they are missing at random. We will examine the missing at random

assumption by assessing differences between dropouts and completers on baseline as well as response variables up to point of premature withdrawal. If the missing at random assumption does not appear to be tenable, we will report the mixed models results but spend additional effort characterizing treatment effect at time of premature withdrawal.

[figure not shown]
Power Analysis and Sample Size Determination:

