The effect of pregnenolone on low back pain will be evaluated using several statistical methods. This clinical trial design will compare two randomly assigned groups (pregnenolone or placebo) with respect to self-reported lower back pain measured on a 0-10 pain scale. Inclusion criteria for the study require that all participants report pain severity of at least 4/10. Given the low back pain often presents as long periods of low-level intensity pain punctuated by periods of acute exacerbation, it is quite likely that the mean pain level for selected participants will substantially exceed 4/10. Thus for power calculations, we assume a baseline mean pain level of six for each group. We also assume a standard deviation of 1.0 since we have little information to support any specific value in this population.

For the purpose of power calculations we assume that the mean pain levels of the two independent groups will be compared using a Two-Sample T-Test, Null Hypothesis: $\text{Mean1}=\text{Mean2}$. Alternative Hypothesis: $\text{Mean1}<>\text{Mean2}$. The standard deviations were assumed to be unknown and equal.

Assuming specified numbers of participants in each group (N) the mean differences detectable for at least 80% power and $\alpha=0.05$ are shown in the following table and figure.

N1	Mean1	Mean2
4	6.0	3.6
5	6.0	3.8
6	6.0	4.0
6	6.0	4.2
8	6.0	4.4
10	6.0	4.6
12	6.0	4.8
17	6.0	5.0
26	6.0	5.2
45	6.0	5.4
100	6.0	5.6

Group sample sizes of 45 achieve at least 80% power to detect a difference of 0.6 between the null hypothesis that both group means are 6.0 and the alternative hypothesis that the mean of group 2 is 5.4 with estimated group standard deviations of 1.0 and 1.0 and with a significance level (alpha) of 0.05000 using a two-sided two-sample t-test. Using this experimental group size should yield sufficient power to detect clinical meaningful effects.

Data Collection: Data pertaining to psychiatric rating and other assessment scales will be collected on hard copy and data pertaining to laboratory values will be collected in manners used for the VA Mid-Atlantic MIRECC Registry. A study number identifying clinical and biological data will be the only number to appear on data and documents used for evaluation or statistical analysis. This data will be kept in locked file cabinets accessible only to qualified personnel.

REFERENCES

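### Fisher's exact test is valid but conservative for the responder and side-effect comparisons; prespecifying Boschloo's test, a baseline-adjusted responder model and risk differences with confidence intervals would recover some power at little cost

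*Combined protocol and SAP*

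**What the plan says.** The Statistical Methods section (under Data Analysis and Statistical Considerations) lists the responder comparison among the secondary analyses: "Categorical analyses of patient response (30% improvement, 50% improvement) will be evaluated via a comparison of proportions using Fisher's exact test". For safety it says "Safety will be assessed by comparing the incidence of major and minor side effects", and the comparison is made "in the study drug vs. placebo groups, using Fisher's exact tests".

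The general decision rule in the same section is two-sided at 0.05: "All tested hypotheses will be considered statistically significant if the 2 sided p value is ≥ 0.05 unless otherwise specified". The inequality is printed the wrong way round; I read it as p ≤ 0.05.

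The target of 45 per arm comes from the Power Analysis section and rests on the continuous pain score alone: "Group sample sizes of 45 achieve at least 80% power to detect a difference of 0.6". Neither section gives an expected responder rate, an expected side-effect rate, or a power figure for either binary comparison. No effect measure or interval is named for them.

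**The concern.** Fisher's test conditions on the total number of events. A 1:1 randomised trial fixes the arm sizes but not that total. With arms this small the conditional distribution is coarse, so the test usually rejects well below 5% of the time under the null, and that unused error rate is lost power. For response, a real benefit is more easily missed. For side effects, a real excess is.

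Two related gaps follow. The responder test takes no account of baseline pain, although the primary model includes it and percentage improvement is measured from it. And if only a p value is reported, the reader cannot see how large a difference the data leave open.

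**Working it through.** **The plan's own figure.** t-test with 45 per arm, difference 0.6, SD 1.0, two-sided 0.05: noncentrality = 0.6 / (1.0 × √(2/45)) = 2.846 on 88 df, critical value 1.987, power 80.4%. The stated figure of at least 80% is reproduced. It says nothing about the binary comparisons.

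**Inputs.** From the documents: 45 per arm (Experimental Design; Power Analysis); two-sided 0.05; up to 120 randomised (Research Design and Methods), hence up to 120/2 = 60 per arm, since the primary analyses include all randomised subjects. Assumed, because none are given: control rates of 5% to 50% and differences of 10 to 35 points, with 2% to 3% added for rare events.

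**Method.** With n per arm and x and y events:

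- Fisher p = sum of C(n,x)C(n,s−x)/C(2n,s) over tables with the same total s that are no more probable than the one observed. Reject at p ≤ 0.05.
- Size at common rate π = sum of Bin(x; n, π) × Bin(y; n, π) over the rejection region. Power uses two different rates.
- Boschloo: reject when Fisher p ≤ c, where c is the largest cut-off that keeps the maximum size over all π at or below 5%. Enumerating every table gives c = 0.0751 at 45 per arm and 0.0665 at 60. Because c exceeds 0.05, Boschloo rejects whenever Fisher does.

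**True size (%) at nominal 5%**

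| Common rate | Fisher, 45 | Boschloo, 45 | Fisher, 60 | Boschloo, 60 |
|---|---|---|---|---|
| 2% | 0.02 | 0.16 | 0.08 | 0.43 |
| 5% | 0.57 | 1.78 | 1.05 | 2.66 |
| 10% | 2.01 | 3.36 | 2.18 | 3.38 |
| 30% | 2.96 | 4.87 | 3.08 | 4.13 |
| 50% | 2.68 | 4.47 | 3.53 | 4.42 |
| Maximum | 3.16 | 4.89 | 3.53 | 4.89 |

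**Power (%) under assumed rates, Fisher → Boschloo** (gains from unrounded values)

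| Rates | 45 per arm | 60 per arm |
|---|---|---|
| 30% vs 55% | 59.0 → 66.0 (+7.0) | 75.0 → 79.7 (+4.7) |
| 20% vs 40% | 46.4 → 54.7 (+8.3) | 60.0 → 64.6 (+4.5) |
| 30% vs 60% | 75.8 → 81.6 (+5.8) | 89.4 → 91.5 (+2.1) |
| 20% vs 50% | 81.5 → 85.9 (+4.3) | 91.3 → 93.5 (+2.2) |
| 5% vs 20% | 48.0 → 55.2 (+7.2) | 62.7 → 67.9 (+5.2) |
| 10% vs 25% | 36.2 → 44.7 (+8.5) | 49.4 → 54.8 (+5.4) |

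Over a 60-point grid at 45 per arm, the gain is 0.8 to 8.9 points (median 5.9). It is 4.7 to 8.9 (median 7.0) where Fisher's power is 30% to 80%, and 0.8 to 4.6 where it exceeds 80%. At 60 per arm the grid gives 0.1 to 6.8 (median 3.3). Rare events fall outside this pattern: 2% vs 10% gains 10.4 points at 45 per arm, but from a power of only 15.1%.

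**An example that needs no assumed rates.** With 0 events against 5 at 45 per arm, Fisher p = 2 × C(45,5)/C(90,5) = 2 × 1,221,759/43,949,268 = 0.0556. Fisher does not reject; Boschloo does (0.0556 ≤ 0.0751).

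**How much sample size matters.** By the usual normal-approximation formula, 80% power needs 82 per arm for 20% vs 40% and 76 per arm for 5% vs 20%. With no events in 45 patients, the two-sided 95% upper bound is 1 − 0.025^(1/45) = 7.9%, whichever test is used.

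**Baseline adjustment.** One simulation of a 30%-improvement endpoint (4,000 trials, 37% vs 63% responding) gave power of 61% for Fisher, 68% for Boschloo and 70% for logistic regression on treatment and baseline pain, with logistic size 5.0% to 5.7%. It assumed a 1.2-point effect and a follow-up SD of 1.8, not the plan's 0.6 and 1.0, so it is illustrative only. The Monte Carlo standard error at 5% is √(0.05 × 0.95/4000) = 0.34 points.

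**The case against.** The strongest reply is that nothing here is wrong. Fisher's test is prespecified, holds its level, and is used only for secondary and safety comparisons in a trial that Research Design and Methods calls a pilot. The primary endpoint has its own model, with baseline pain in it. That stands.

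Three further replies also stand. The gain depends on rates that the documents do not supply and on how many patients are analysed. Boschloo is itself conservative for uncommon side effects: 1.8% at a 5% rate and 0.16% at 2%, with 45 per arm. And more rejections mean more false positives, although for Boschloo still within 5% per test; the plan states no multiplicity adjustment for these comparisons.

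A reader might infer that both comparisons lose a fixed 6 to 9 points. The documents do not support that, because they give no rates and allow up to 120 randomised. A reader might also infer that a non-significant side-effect test will be presented as evidence of safety. The plan says no such thing, and comparing incidence does not preclude reporting rates and intervals.

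What the reply does not supply is a reason to prefer Fisher's test when an exact test with the same ceiling rejects at least as often.

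**Conclusion.** The point holds as an efficiency improvement. At 45 per arm Fisher's true size is about 0.6% to 3.2% for rates of 5% to 50%. Replacing it with Boschloo's test typically adds 5 to 9 points of power where Fisher's is 30% to 80%, less than 5 points above that, and about 2 to 5 points in the tabulated scenarios at 60 per arm. The size figures follow from the arm size alone; the power figures rest on assumed rates.

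Two stronger readings fail. The planned analysis is not invalid, since Fisher's error rate is below 5%, not above it. Nor would the change make these comparisons well powered: at 45 per arm Boschloo still reaches only 54.7% for 20% vs 40% and 44.7% for 10% vs 25%. Sample size is the main limit.

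**What to change.** Before unblinding, amend the secondary-analysis and safety text of Statistical Methods as follows:

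- Replace Fisher's exact test with Boschloo's unconditional exact test, two-sided at 5%, for the 30% and 50% responder comparisons and for side-effect incidence.
- Analyse each responder endpoint with a logistic model containing treatment and baseline pain, reported as a standardised risk difference with a 95% confidence interval. State in advance that the Boschloo p value decides significance and that the model supplies the adjusted estimate, so that two p values do not compete.
- Report side-effect incidence by arm as a risk difference with a 95% confidence interval, and interpret non-significant results through the interval.

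The cost is a paragraph of wording and a few lines of code. The true false-positive rate moves closer to 5%, though for Boschloo not above it. The logistic test is a large-sample method whose size may slightly exceed 5%. The guarantee of rejecting whenever Fisher does belongs to Boschloo's test and should not be assumed for Barnard's or for the logistic model.

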Significance: There is an acute and immediate need for the development of safe, effective, and non-habit forming pharmacological treatments for chronic pain disorders. Very large numbers of OEF/OIF Veterans report chronic pain symptoms (as many as 50% or higher). Current medications such as opiates that are frequently used to treat chronic pain symptoms have side effect risks such as respiratory depression, addiction, sedation, and potentially lethal interactions with other drugs. The proposed projects could lead to new therapeutic avenues that are safe, non-habit-forming, and effective. Neurosteroids demonstrate pronounced analgesic actions, and preclinical and clinical data suggest that these molecules hold promise for chronic pain disorders. New agents for the treatment of chronic pain could markedly improve long-term outcome and quality of life in OEF/OIF Veterans.

Relevance to Veteran Health: There is currently a paucity of safe and effective agents for the treatment of chronic low back pain, a disorder that impacts large numbers of OEF/OIF Veterans and is frequently accompanied by PTSD and other comorbid symptoms. Pregnenolone may represent an effective, safe, well-tolerated, immediately accessible, and inexpensive treatment for these symptom domains, potentially leading to improved functional outcome and quality of life in OEF/OIF Veterans with chronic pain disorders.

RESEARCH DESIGN AND METHODS

The proposed randomized controlled trial (RCT) will investigate adjunctive pregnenolone as a potential analgesic in OEF/OIF Veterans with chronic low back pain. This will be a 4-week, randomized, double-blind placebo-controlled pilot study preceded by a one-week placebo lead-in period (all participants). Proposed sample size estimates are 45 patients per group (it is estimated that up to 120 Veterans will be randomized in order to obtain the sample size of 45 participants per group).

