1. Referred patients and patients responding to IRB-approved advertisements or IRB-approved recruitment letters, phone calls (with IRB-approved phone script), will meet with a member of the research team to discuss the study and the risks and benefits of participation. In addition, patients will be screened for exclusion and inclusion criteria. If subjects are interested, the informed consent document will be discussed with them. Patients will have the option of taking the informed consent with them and discussing the matter with family, friends or clinicians. If the patient is followed by a psychiatrist, the psychiatrist will be consulted prior to randomization regarding the patient's appropriateness for enrollment in the study.

2. Once the informed consent is signed, the subject will proceed to the initial screening procedures. First, patients will receive a more detailed assessment than what was queried on the telephone pre-screening interview to determine whether they meet qualifications to participate in the study.
3. We will then determine whether subjects are in good health. A research physician will examine patients before starting the study. Patients will have a venous puncture for laboratory testing (please see Schedule of Events). Subjects will receive an ECG at Visits #1 and #6. Since patients may be on antidepressant and occasionally on antipsychotic medicines (treatment-as-usual), it is part of routine clinical care to receive an ECG at least once each year on these agents. A follow-up ECG at Visit #6 will be performed to confirm that there are no changes in ECG tracings (since there is one report of palpitations in the existing scientific literature following pregnenolone). Patients with significant abnormal physical exam, blood tests, or ECG will be excluded from the study and referred to their primary care provider.

Table 1. Study Schedule

Visit	1	2	3	4	5	6	Follow Up	Follow Up
	Screen	Baseline					Phone	Phone
Week	0	1	2	3	4	6	7	8
Inclusion/Exclusion (5 min)	X							
Informed Consent (15 min)	X							
Demographics (10 min)	X							
Medical History (10 min)	X							
Psychiatric Diagnosis (MINI) (15 min)	X							
Physical Exam and ECG (30 min)	X						X	
Vital Signs (5 min)	X	X	X	X	X	X		
Urine Collection: (5 min)								
Drug Screen	X	X		X			X	
Urinalysis	X	X	X	X	X	X		
Urine Pregnancy Test (females only)	X	X	X	X	X	X		
Concomitant Medications (5 min)	X	X	X	X	X	X		
Patient Pain Diary (5 min)	X	X	X	X	X	X		

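### The only planned between-arm safety analysis is Fisher's exact tests of side-effect incidence, with no effect estimate or interval, so a non-significant result could not by itself support a statement of no excess risk for uncommon side effects

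*Combined protocol and SAP*

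**What the plan says.** The between-arm safety analysis is one sentence among the secondary analyses in Data Analysis and Statistical Considerations, Statistical Methods: "Safety will be assessed by comparing the incidence of major and minor side effects", to be done "in the study drug vs. placebo groups, using Fisher's exact tests". The terms major and minor are "defined in human subjects section below"; that definition is not in the text available for this review.

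The same section sets one rule for all tests: "All tested hypotheses will be considered statistically significant if the 2 sided p value is ≥ 0.05 unless otherwise specified". The inequality is printed the wrong way round. I read it as p < 0.05.

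Experimental Design gives the group sizes: "45 subjects will receive pregnenolone, and 45 subjects will receive placebo for 4 weeks". Research Design and Methods calls the study a pilot and expects up to 120 Veterans to be randomised to reach 45 per group. Subject Recruitment describes the 120 as enrolled. Power Analysis and Sample Size Determination covers only a 0.6-point pain difference.

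Safety data collection is extensive. There is an adverse event form at Visits 2 to 6 with calls at Weeks 7 and 8, laboratory tests, vital signs and a suicidality scale at each visit, ECGs at entry and completion, and physician review of laboratory results and ECGs within 24 hours.

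**The concern.** A test of no difference can show harm. Failing to reject shows nothing unless the test had a good chance of detecting a harm worth knowing about, or an interval shows which harms are excluded. The plan provides neither for safety: the sample size was not chosen for it, and no estimate or interval is specified.

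This matters because safety is part of the case for the drug. The Significance section hopes that "The proposed projects could lead to new therapeutic avenues that are safe, non-habit-forming, and effective". The individual monitoring protects participants, but it yields no between-arm estimate. Followed as written, the analysis gives a set of p values, and a reader could not tell from a non-significant one how large an excess of side effects remains possible.

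**Working it through.** **The plan's own figure.** For pain, with a difference of 0.6, SD 1.0, 45 per arm and two-sided alpha 0.05, the noncentrality is 0.6 × √(45/2) = 2.85 on 88 degrees of freedom, with critical value 1.987. Power is 80.4%, which agrees with the stated at least 80%. There is no safety figure to reproduce.

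**Inputs for safety.** The test (Fisher's exact, two-sided, p < 0.05) is from Statistical Methods. The 45 per arm is from Experimental Design. The 60 per arm is 120/2, from Research Design and Methods, and applies only if all 120 are randomised. The documents name side effects without frequencies, so every rate below is an assumption.

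**Method.** For n per arm, enumerate every pair of event counts (a, b) from 0 to n and mark those with Fisher p < 0.05. Then

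miss rate = 1 − Σ Bin(a; n, p_drug) × Bin(b; n, p_placebo), summed over the marked pairs.

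| Assumed placebo vs pregnenolone rate | Missed, 45 per arm | Missed, 60 per arm |
|---|---|---|
| 5% vs 10% | 94% | 91% |
| 5% vs 15% | 77% | 67% |
| 10% vs 20% | 82% | 75% |
| 10% vs 30% | 43% | 27% |
| 20% vs 40% | 54% | 40% |
| 20% vs 60% | 3% | 1% |

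The ratio of the rates does not fix the miss rate. A tripling is missed 77% of the time from 5% but 3% of the time from 20%. Low power is confined to uncommon side effects and moderate excesses. With no placebo events and 45 per arm, 5 events on pregnenolone give p = 0.056, so at least 6 are needed for significance (p = 0.026).

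**What an interval adds.** Take 8/45 on pregnenolone and 2/45 on placebo, an invented result.

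- Fisher p = 0.090, so not significant.
- Risk difference = 17.8% − 4.4% = 13.3 percentage points.
- Wilson 95% limits: 9.3% to 31.3% on pregnenolone, 1.2% to 14.8% on placebo.
- Newcombe lower limit = 13.3 − √[(17.8 − 9.3)² + (14.8 − 4.4)²] = −0.1 points.
- Newcombe upper limit = 13.3 + √[(31.3 − 17.8)² + (4.4 − 1.2)²] = +27.3 points (unrounded inputs).

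The p value alone records no significant difference. The interval shows that an excess of about 27 percentage points is not excluded.

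**No events in an arm.** The exact two-sided 95% upper limit for 0/45 is 1 − 0.025^(1/45) = 7.9%.

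**The case against.** The strongest reply has five parts.

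1. *No rule says that a null test means safe.* This stands. A reader might infer that non-significance would be declared as safety, but the plan contains no such rule, and the sentence in the Significance section is a background aspiration. What remains is that the plan specifies no other basis for a comparative statement.
2. *Safety is not judged by Fisher's test alone.* This also stands. Monitoring of individuals is substantial. The point is limited to the between-arm statistical analysis.
3. *Power depends on rates that nobody has stated.* Correct. A reader might take the miss rates as a general property of the design for any doubling or tripling, and the table shows that they are not. If major and minor side effects are pooled categories, their rates could be higher than those of a single side effect, where Fisher's test does better. The safety set could also approach 60 per arm. Both soften the figures, but at 60 per arm 5% versus 15% is still missed in two trials out of three.
4. *It is a pilot, so low safety power is expected.* Agreed, and no extra patients are asked for. Low power is the reason to report estimates with intervals.
5. *Comparing incidence already implies per-arm percentages, from which anyone can compute an interval.* Partly true, and it is why the fix is cheap. It does not make the plan specify the interval or how to interpret it.

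A reader might also see the same weakness in the ECG sentence of the Study Timeline: "A follow-up ECG at Visit #6 will be performed to confirm that there are no changes in ECG tracings". In context that is the reason for a per-patient clinical check, prompted by one published report of palpitations. It is not a statistical claim and needs no change on this ground.

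**Conclusion.** The point holds in a limited form. Fisher's exact tests at a 0.05 rule are the only planned between-arm safety analysis in the text available, and no effect estimate or interval accompanies them. For uncommon side effects, a non-significant result could not by itself support a statement of no excess risk. Under assumed rates of 5% versus 15% and 10% versus 20%, the excess is missed in 77% and 82% of trials at 45 per arm, and in 67% and 75% at 60 per arm. For common side effects with a large excess, the test performs adequately (20% versus 60% is missed in 3% of trials or fewer).

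This rests on assumed event rates, on reading the printed inequality as p < 0.05, and on the unseen definition of major and minor not adding an analysis. The documents do not support the stronger readings that the plan equates non-significance with safety, or that one miss rate describes the design. It is a worthwhile, inexpensive improvement and not a flaw in the conduct of the trial.

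**What to change.** Replace the safety sentence in Statistical Methods with wording such as:

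*For any major side effect, any minor side effect and each individual side effect, we will report the number and percentage of participants per arm and the pregnenolone-minus-placebo risk difference with its 95% confidence interval (Newcombe or Miettinen-Nurminen). Where an arm has no events, the exact 95% upper limit for that arm will be given. Fisher's exact p values will be descriptive. A non-significant difference will not be taken as evidence of no excess risk.*

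Make sure that the definition of major and minor can be found from that sentence.

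The change needs no new data, visits or participants. The one small downside is a less favourable safety statement, because the report must say which excess rates were not excluded.
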